#### **4.4.2 Screening and Eligibility Assessment**

Consecutive ECD kidneys that are offered to the participating transplant centres for transplantation will be included in the study. Potential recipients will be informed and consented.

Laboratory tests will include blood samples that will be taken as part of standard follow-up.

#### **4.4.3 Baseline Assessments**

The paper version of the EuroQol EQ-5D-5L questionnaire will be completed at the time of consenting the patient to the trial (Appendix D). Here, index-based values are recorded, in order to facilitate calculation of quality-adjusted life years or months of patient survival, that are used to make a health-economic evaluation. The questionnaire will be completed again at 3 and 12 months. Patients who are not willing to complete this questionnaire, will not be excluded from the study.

Donor and recipient demographics will be recorded as per CRF form.

#### **4.4.4 Randomisation**

##### **4.4.4.1 Allocation: Sequence generation**

Recruiting site personnel will be responsible for randomisation of individual kidneys. Kidneys will be randomly assigned to either cold storage or machine perfusion group with a 1:1 allocation as per a computer generated randomisation schedule held centrally by the trial office. The allocation will be stratified by centre.

##### **4.4.4.2 Allocation: Concealment mechanism**

Allocation concealment will be ensured by use of central computerised randomisation (with telephone backup). Allocation will not be revealed until the patient has been recruited to the trial and donor and recipient baseline characteristics have been recorded. Random permuted block length will be used; block sizes will not be disclosed

##### **4.4.4.3 Implementation**

Recruiting site personnel will log in to an online data collection and randomisation tool once all criteria for inclusion have been checked. The allocation sequence will be generated on a web-accessible server by the Surgical Intervention Trials Unit (SITU), University of Oxford.

#### **4.4.4.4 Blinding**

Transplant participants will be blinded.

Care providers will not be blinded for the treatment arm.

Routine laboratory parameters will be analysed in the central university laboratory not knowing about the allocation to the study groups

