## 4 TRIAL DESIGN

### 4.1 SUMMARY OF TRIAL DESIGN

The study will be conducted as a prospective, randomized, parallel group, single blinded, controlled, multi-centre, non-paired superiority trial; allocation will be on a 1:1 basis and an intention-to-treat method will be used to analyze the results.

After accepting the potential ECD organ for donation, kidneys will be allocated following the standard Eurotransplant/ UK-transplant allocation rules.

In a non-paired-design, each ECD kidney that has been accepted for transplantation by one of the participating centres will be randomly assigned to SCS or to SCS followed by reconditioning by end-ischemic oxygenated HMP (HRMP+O2). Randomizing kidneys after they have been accepted for transplantation avoids a potential bias that acceptance of the kidney is being influenced by the preservation modality.

[figure not shown]

If two kidneys are accepted for transplantation by the same centre the surgeon will decide which kidney to transplant first according to their local protocol.

It is not essential for both kidneys from a donor to enter the trial. If only one of the kidneys is deemed transplantable, it can still be included in the trial analysis.

Exceptionally anatomical situations may not allow connection of a kidney to the perfusion circuit. In this situation the kidney should be preserved by cold storage alone even though it was randomized to HRMP+O2.

Anticipated flow of patients through the trial is depicted below

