### **4.2.2 Secondary outcome measures**

- Patient and (death censored) graft survival at day 7, 3, 6 and 12 months after transplantation. eGFR defined by the MDRD equation at day 7, 3, 6 and 12 months after transplantation.
- DGF defined as the need for dialysis in the first 7 days after transplantation and preceding the return of kidney function.
- SGF based on functional DGF defined as the absence of decrease in the serum creatinine level of at least 10% per day for at least 3 consecutive days in the first 7 days after transplantation.
- PNF defined as the continued need for dialysis at 3 months after transplantation.
- Comparison of biopsy proven acute rejection between the 2 groups.
- Quality of life measures (EQ-5D-5L) at consent, 3 and 12 months, length of hospital stay (including ICU) and need/length for dialysis treatment

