## **6 STATISTICS**

### **6.1 DESCRIPTION OF STATISTICAL METHODS**

The primary analysis of the trial will be an intention-to-treat analysis comparing intervention (HRMP) against control (SCS) for all primary and secondary outcomes. The primary endpoint, one year graft survival, will be analysed using logistic regression with adjustment for stratification factors. Additional analyses adjusting for other important prognostic factors will also be undertaken. Binary outcomes will be assessed using chi-squared tests and logistic regression to adjust for prognostic factors. Continuous outcomes will be compared using the T-test if normally distributed, otherwise using the Mann-Whitney U test. Time-to-event outcomes will be analysed using survival analysis methods, including Kaplan-Meier plots and Cox proportional hazards regression model with calculation of hazard ratios. Outcomes will be reported with 95% confidence intervals and two-sided p-values to 3 decimal places.

A secondary analysis of the primary endpoint will be done as per protocol.

A Statistical Analysis Plan (SAP) containing a detailed description of the statistical methods will be drafted as a separate document early in the trial and finalised prior to the final data lock.

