## **6.2 NUMBER OF PARTICIPANTS**

### Sample size calculation

Based on the previously published paper by Treckmann et al., the 1-year graft survival for ECD kidneys preserved by SCS is being estimated at 80%. The use of HRMP is being hypothesized to improve 1-year graft survival from 80% to 92% based upon the improvement in graft survival of ECD kidneys seen in the MP Trial.

For a power of 80% with Type I error (alpha) of 5%, in a two-sided statistical model, the required sample size to detect an improvement in 1-year graft survival from 80% to 92% is 131 kidneys in each treatment arm, 262 in total.

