#### **10.2 DATA COLLECTION METHODS**

Data collection will be achieved using secure internet-based forms. Data will be input by local lead investigators/coordinators trained in the use of the system prior to receiving log-in details. Data will be uploaded to a central database maintained by the database manager at the SITU. Demographic data, laboratory results and survival data will be recorded locally on the data collection system. Pre-transplantation, 3 and 12-month quality of life data from the EQ-5D-5L and details of resource utilisation will also be recorded.

All blood samples will be analysed in local laboratories and results recorded in common units.

Biopsies taken by centres as part of their protocol will be split, with a portion being analysed locally, and the other portion analysed centrally as part of the COPE bio-resource (WP7) and the biopsy scores recorded in the main database.

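### Randomisation is stratified by centre, but the test fixed for eGFR has no centre term, so its confidence intervals are somewhat too wide; the two statements on the laboratory should also be reconciled

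*Protocol*

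**What the plan says.** **Allocation.** Section 4.4.4.1: "The allocation will be stratified by centre". Section 4.4.4.2 adds random permuted blocks, and section 4.1 sets the ratio: "allocation will be on a 1:1 basis and an intention-to-treat method will be used to analyze the results".

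**Analysis.** Section 6.1 handles the primary endpoint and continuous outcomes differently.
- Primary endpoint: "The primary endpoint, one year graft survival, will be analysed using logistic regression with adjustment for stratification factors".
- Continuous outcomes: "Continuous outcomes will be compared using the T-test if normally distributed, otherwise using the Mann-Whitney U test". No centre term is mentioned.

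**Outcome affected.** Section 4.2.2 lists "eGFR defined by the MDRD equation at day 7, 3, 6 and 12 months after transplantation". This is calculated from serum creatinine, which Appendix B schedules at all four of these times.

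**Laboratory.** Section 4.4.4.4, on blinding: "Routine laboratory parameters will be analysed in the central university laboratory not knowing about the allocation to the study groups". Section 10.2, on data collection: "All blood samples will be analysed in local laboratories and results recorded in common units".

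**The concern.** Balancing the arms within each centre removes centre differences from the treatment contrast. An unadjusted t-test does not take account of this: its pooled standard deviation still contains the spread between centres, so the reported standard error exceeds the true sampling error of the estimate. The sources of that spread are case mix, local practice and, if creatinine is measured locally, the assay. Common units do not make assays agree.

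What is at stake is precision and power for a secondary outcome analysed at four time points. The protocol adjusts for the stratum in its primary analysis and omits it here, although the same reasoning applies.

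The laboratory wording is a second, smaller matter. Care providers are unblinded under section 4.4.4.4, so the laboratory sentence is the only blinding stated there beyond the participants. It should describe the laboratories that produce the results.

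**Working it through.** **The protocol's own figure.** The protocol states no sample size or power for eGFR. Its one calculation is for graft survival, 80% versus 92%: "For a power of 80% with Type I error (alpha) of 5%, in a two-sided statistical model". With pooled variance and no continuity correction,

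n = [1.960 × √(2 × 0.86 × 0.14) + 0.842 × √(0.80 × 0.20 + 0.92 × 0.08)]² / 0.12² = 130.1, rounded up to 131 per arm.

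This reproduces the stated 131 and is unaffected by what follows.

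**Inputs for eGFR.**
- Total 262, allocated 1:1 in permuted blocks within centre (sections 4.1, 4.4.4 and 6.2).
- Centre weights from section 6.3: 40, 30-45, 35-40 and 20 per year. The midpoints 40, 37.5, 37.5 and 20 give centres of 78, 73, 73 and 39 (263 after rounding).
- s, the share of eGFR variance lying between centres. The protocol does not give it, so 5%, 10% and 20% are assumed.

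**Formulas.** Set the total variance to 1. With balance within centres, the treatment difference has variance proportional to 1 − s, while the t-test estimates variance proportional to 1. Hence:
- Ratio of reported to true standard error: r = 1/√(1 − s).
- True two-sided type I error: 2 × [1 − Φ(1.96 × r)].
- Power of the t-test for an effect that the centre-adjusted model detects with 80% power: Φ(0.842 + 1.96 − 1.96 × r).

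| s | r | 1.96 × r | Type I error, formula | Type I error, simulated | t-test power against 80% adjusted |
|---|---|---|---|---|---|
| 0.05 | 1.026 | 2.011 | 4.4% | 4.6%, 4.9% | 78.5% |
| 0.10 | 1.054 | 2.066 | 3.9% | 3.6%, 4.0% | 76.9% |
| 0.20 | 1.118 | 2.191 | 2.8% | 3.0%, 3.2% | 72.9% |

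The simulated columns come from two simulations: 8,000 runs per setting with centres of 78, 74, 74 and 40, and 6,000 null runs per setting with 78, 73, 73 and 39 and blocks of 4 and 6. The centre-adjusted model stayed between 4.8% and 5.5% in both. In the second simulation the interval width ratios were 1.026, 1.055 and 1.119, matching r. At s = 0.20 the t-test's mean reported standard error was 0.123 SD against an actual 0.112 SD, and coverage was 96.8%. At s = 0.02 the intervals were only 1% too wide.

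**Power.** By the formula the loss is 1.5, 3.1 and 7.1 points. With the true difference fixed at an assumed 0.35 SD, simulated power was 80.3% versus 81.5%, 82.2% versus 84.6%, and 84.1% versus 88.8%, losses of 1.2, 2.4 and 4.7 points. The loss is smaller there because the adjusted model already has more than 80% power.

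These figures are for the t-test. The Mann-Whitney alternative also ignores the stratum, but its loss was not computed.

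**The two laboratory statements.** One places routine laboratory analysis in a single, unnamed central university laboratory; the other places every blood sample in local laboratories. Section 4.4.2 takes laboratory tests from standard follow-up blood, so both statements cover the creatinine behind eGFR. As worded they conflict.

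**The case against.** - **The effect is small and conservative.** This stands. The estimate is unbiased and type I error is not inflated. Below a between-centre share of about 10% the excess width is 5% or less, and nothing in the protocol shows that the share is larger.
- **The detail belongs in the SAP.** This stands in part. Section 6.1 promises a separate SAP, which may add centre, and it mentions additional adjusted analyses. But the protocol itself names the test for continuous outcomes and names it without the stratum, so a SAP that adjusts for centre would depart from the stated method.
- **The laboratory wording may be only loose.** This is a fair reading. The phrase could mean each hospital's own central laboratory. Follow-up under local protocols (section 4.6) and the absence of any creatinine shipment in Appendix A point that way. The protocol does not say so, however, and section 10.2 separates local from central analysis where it describes biopsies.

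A reader might go further on the laboratory. One stronger inference is that the laboratory blinding does not exist; but section 10.2 nowhere says that local laboratories learn the allocation. Another is that assay differences drive the loss of precision; but the calculation uses a total between-centre share and assigns none of it to laboratories. With a single laboratory, case mix and practice would still differ between centres. Nor does the protocol rank eGFR above the other secondary outcomes.

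**Conclusion.** The point holds as a modest loss of precision. The protocol stratifies by centre and then fixes an eGFR comparison that ignores centre, so its intervals are too wide and its test conservative. The excess width is about 3%, 5% or 12% if 5%, 10% or 20% of eGFR variance lies between centres, with roughly 2 to 7 points of power lost. The direction follows from the design. The size rests on an assumed share and on the centre sizes in section 6.3. The treatment estimate, the primary analysis and the sample size of 262 are unaffected.

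The laboratory statements are a separate point of wording. They conflict as written and need one consistent description, but they do not show that blinding is lost.

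**What to change.** 1. In section 6.1, and in the SAP, replace the t-test or Mann-Whitney test for eGFR with a linear model containing treatment and centre. Use log eGFR or robust standard errors if the distribution is skewed.
2. Note the limit of this remedy. Section 5 has some participants return to referring centres, so later creatinine values may come from further laboratories, and a transplant-centre term may not remove all of that variation.
3. State in both 4.4.4.4 and 10.2 which laboratories measure creatinine, and word the blinding sentence to match. If analysis is local, record the laboratory and the creatinine assay.

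The cost is wording in the protocol and SAP. Centre is already recorded as the stratum, and no extra patients or samples are needed. Recording the laboratory and assay would add a small data item.

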#### **4.4.4.5 Emergency unblinding**

No formal procedure will be established for the un-blinding of participants. None of the possible complications potentially related to the preservation method (e.g. discarding a kidney, primary non-function) require the absolute need for the participant to know the allocation arm in order to treat them in the best way. All adverse events will be collected and reported.

### **4.5 TRIAL INTERVENTIONS**

#### **4.5.1 Machine perfusion study group**

Kidneys initially stored on ice and randomized to HRMP will be placed on the Kidney Assist device (Organ Assist, Groningen, The Netherlands) as soon as possible upon arrival in the transplant center. Arrival time of the kidney on SCS at the transplant center as well as start of perfusion time will be recorded.

The Kidney Assist –manufactured and dispersed by Organ Assist (Groningen, the Netherlands)– is a CE marked medical device designed for isolated hypothermic oxygenated perfusion of a donor kidney during storage. More information on the Organ Assist device can be found in the instruction manual, or on their website [www.organ-assist.nl](http://www.organ-assist.nl). The renal artery is connected to a cannula and a cold preservation solution (perfusate) is pumped through the kidney while adding oxygen to the perfusate. The Kidney Assist uses a 0.6 litre oxygen cylinder with a pressure of 300 bar. The flow will be set at 100 ml/min. The Kidney Assist pumps the perfusate through the kidney vasculature in a pulsatile way (60 bpm). The Kidney Assist pump is pressure controlled. The pressure can vary from 0 to 60 mmHg according to the chosen setting. The pressure will be set at 25 mmHg and cannot be modified during the preservation of the kidney unless the Kidney Assist gives a ‘flow alarm’. The ‘flow alarm’ is activated when the flow limit of the Kidney Assist is reached (500 mL/min). The set pressure

will then be automatically decreased to a lower value. At this point the connection of the kidney with the Kidney Assist will be checked to rule out any problems with the connection (e.g. leak of perfusion fluid) that can explain the high flow. If no reason for the high flow can be found, then the lower perfusion pressure will be accepted and noted in the eCRF.

Perfusate and kidney are cooled to 0-4°C using crushed ice outside the sterile container. The Kidney Assist continuously registers renal resistance and flow measures.

All kidneys will be perfused with Belzers Machine Perfusion Solution.

Organ Assist will provide training on the use of the machine in all participating centres.

For more details on the Organ Assist device please see Appendix E

In order to allow marginal kidneys to be connected to the perfusion pump as long as possible after arrival at the transplant center, kidneys will be completely prepared for transplantation prior to being placed on the device, if possible. This will allow keeping the kidney on the pump until the recipient vasculature has been completely prepared for implantation of the organ. If applicable, cross-match testing will be performed during machine perfusion time, which is expected to allow a minimum perfusion time of at least 2 hours. In case of a positive cross match or a medical reason due to which the patient cannot undergo transplantation, the kidney will be re-allocated. The accepting transplant center will be able to choose whether they would like the kidney to be transported while connected to the perfusion machine or prefer the kidney to be disconnected from machine perfusion, in which case, the kidney will be placed in cold storage solution.

Use of machine preservation should not prolong the total ischemia time. Total perfusion time as well as total cold ischemia time (CIT) will be recorded.

Perfusion measurements will not be used for accepting/ discarding kidneys. In order to verify whether the kidney is being adequately perfused, the study coordinator will record perfusion flow and renal resistance (RR) at 15 minutes after initiation of perfusion. Any necessary corrective actions will be recorded (check for leakages, obstructions, re-cannulation, etc). Also at the end of perfusion, final flow, RR and temperature will be recorded by the study coordinator. All machine perfusion data will be downloaded at the end of each case. Perfusion parameters such as flow and renal vascular resistance will be hidden to the transplant team. The study coordinator will not be directly involved with recipient care.

#### **4.5.2 Static cold storage (control) group**

Control kidneys will be treated according to usual procedures of cold preservation.

No specific preservation solution for SCS will be mandated; type of SCS preservation solution used will be recorded.

After flush out upon retrieval with ice-cold preservation solution the organs will be shipped on ice submerged in the respective solution and transplanted in the implantation center using established standard procedures.

Included participants will receive immunosuppressive regimens according to the standard treatment of their respective transplant centres.

#### **4.6 ANCILLARY AND POST-TRIAL CARE**

All participants will be monitored as per normal practice for the participating centres.

Patients will be followed up as per the local protocol.

A schedule of study procedures can be found in Appendix B.

#### **4.7 DEFINITION OF END OF TRIAL**

The end of the trial is the date of the last visit at one-year post transplant of the last enrolled recipient.

#### **4.8 WITHDRAWAL OF PARTICIPANTS**

The participant will be advised in the consent forms that they have the right to withdraw from the study at any time without prejudice, and may be withdrawn at the discretion of the Investigator at any time.

Reasonable effort should be made to contact any subject lost to follow up during the course of the trial in order to complete assessments and retrieve any outstanding data.

As this randomised controlled trial does not intervene with the patient, we would only expect withdrawals to be due to the patient withdrawing their consent for us to access their data, or if they are lost to follow-up.

The reason for withdrawal will be recorded in the CRF.

If the participant is withdrawn due to an adverse event, the investigator will arrange for follow-up visits or telephone calls until the adverse event has resolved or stabilised. In case the recipient gives consent, is included in the study but then loses capacity during the running of the trial, first degree relatives or the recipients medical proxy will be able to withdraw consent.

## **5 SAFETY REPORTING**

Reporting of all Serious Adverse Events will be done in accordance with the European Commission Guidelines on Medical Devices Serious Adverse Event Reporting (MEDDEV 2.7/3; December 2010).

It is the responsibility of the local investigator to ensure that all adverse events which fall in to the category of Serious Adverse Events (SAEs) and any device deficiencies (including Serious Adverse Device Effects (SADEs)) are reported to the coordinating centre, chief investigator, principle investigator, national investigators as soon as possible after becoming aware of the event but no later than 24 hours.

Adverse event and serious adverse event reporting will be via the electronic data collection tool using the COPE SAE form, with SAEs being automatically forwarded to the Trial Coordinator and clinical reviewers by the reporting tool. The clinical reviewers are the Chief Investigator, Principle Investigator and Central Investigator and National Investigators. Reporting by Fax will provide a backup system ([name]) in the event that the online data collection tool is unavailable. The Fax machine is located in the central coordinating centre and is manned during normal office hours only.

Within the following 5 working days, the Local Investigator should provide any additional information on the initial SAE or device deficiency in the form of a written narrative using the same SAE form submitted initially – do not create a new form for follow up information. This should include a copy of the completed SAE form, and any other diagnostic or relevant information that will assist the understanding of the event. Significant new information on ongoing serious adverse events should be provided promptly to the coordinating centre and clinical reviewers using the same electronic COPE SAE form.

On submission of an electronic SAE form, the co-ordinating centre and all of the clinical reviewers will be immediately notified by email. They will review SAEs and, if they feel they pose an immediate risk to patient health or safety, then they will report them to the DMC immediately and to the device manufacturer and research ethics committees within 2 calendar days of the principle Investigator becoming aware of the event.

All other reported SAEs will be reported to the DMC within 7 calendar days of notification, if appropriate. This will not include SAEs that may be expected as part of the risks of kidney transplant surgery. Adverse device events (SADEs, USADEs) and device deficiencies will also be reported to the device manufacturer. All SAEs will be followed up to resolution. The DMC will review the accumulating data at regular intervals.

SAE reporting will continue until completion of follow up at 1 year after transplantation. Participants transferred back for on-going care to referring centres will have their data including AEs related to the outcome measures collected by data collection forms sent to the participant's specialist. Participant cards will be provided to all participants of the study, with a contact telephone number (research nurse/ researcher) to inform regarding the occurrence of SAEs.

The Principle Investigator will also inform all investigators concerned and the device manufacturer of relevant information about USADEs that could adversely affect the safety of participants.

